**Exclusion Criteria**

The exclusion criteria for enrolment are:

1. Patients with the following contraindications:
  - Hypersensitivity to the active substance or to any of the excipients.
  - Patients with severe aortic stenosis, patients with systolic blood pressure  $< 100$  mm Hg, and patients with heart failure class NYHA III and NYHA IV.
  - Patients with prolonged QT at baseline (uncorrected  $> 440$  msec), or severe bradycardia, sinus node dysfunction or second degree and third degree heart block in the absence of a pacemaker.
  - Use of intravenous rhythm control antiarrhythmics (class I and class III) within 4 hours prior to, as well as in the first 4 hours after, BRINAVESS™ administration.
  - Acute coronary syndrome (including myocardial infarction) within the last 30 days.
2. Enrolment in an investigational drug or device clinical trial in the 30 days prior to study enrolment. Participation in another non-interventional drug or device study or registry is permitted.

**Post-Authorisation Safety Study (PASS) Study****Appendix I****Calculation of Enrolment Rates Post Amendment 2 Approval**

The table below shows an estimate of enrolment per country to enroll 810 patients and reach the 2000 patient recruitment target by Q4 2017.

Country	2015 average enrolment rate (pts/site/month)	Number active sites	Number pts to be enrolled		Enrolment rate post protocol amendment (pts/site/month)	Total number pts to be enrolled
			Prospectively	Retrospectively		
Austria	1.1	8	110	0	1.1	110
Denmark	1.1	1	15	0	1.1	15
Germany	0.4	8	55	0	0.4	55
Spain	0.6	7	60	20	0.8	80
Sweden	0.8	3	35	70	2.0	105
Finland (enrolment to start Jan 2017)	-	5	100	345	10	445
Total	0.64	33	375	435	3.4	810

**Vernakalant IV Sterile Concentrate Prospective Safety Registry Study**

Sponsor Protocol Identifier: 6621-049-00

3 August 2016

---

Market Uptake of Brinavess

Vials sold per year since study started in 2011.

	No. vials sold 2011	No. vials sold 2012	No. vials sold 2013	No. vials sold 2014	No. vials sold 2015
Austria	705	844	537	919	1105
Denmark	120	117	118	130	70
Spain	60	326	139	360	529
Sweden	311	568	435	752	896
Germany	1773	1000	442	647	548
Finland	655	813	336	761	1320

**Vernakalant IV Sterile Concentrate Prospective Safety Registry Study**

Sponsor Protocol Identifier: 6621-049-00

3 August 2016

---

1. OVERVIEW OF STUDY DESIGN

This is an observational single-exposure cohort PASS (no study intervention or mandated procedures) of patients administered vernakalant intravenous (IV) within clinical sites across European Union (EU) member countries. Participating countries include Denmark, Sweden, Germany, Austria, Spain and Finland. Patients enrolled in the study received vernakalant IV at the discretion of their physicians and were followed for 24 hours after the last vernakalant IV infusion or until discharge/end of medical encounter, whichever occurred first, for health outcomes of interest (HOIs) and serious adverse events (SAEs). No follow-up visits or examinations, laboratory tests, or procedures are mandated as part of this study.

2 OBJECTIVES

2.1 Primary Objectives

The primary objectives of the study are to:

1. Estimate the incidence of the following medically significant HOIs reported during treatment and during the first 24 hours after last infusion of vernakalant IV or until discharge/end of medical encounter, whichever occurs earlier: significant hypotension, significant ventricular arrhythmia (sustained ventricular tachycardia (VT), Torsades de Pointes, ventricular fibrillation), significant atrial flutter, and significant bradycardia.
2. In order to investigate the potential risk of overdose and medication error, describe vernakalant IV administration/dosing by summarising patient body weight, total dose with each intravenous (IV) infusion, and length of time for each IV infusion.
3. To evaluate the effectiveness of the risk minimisation activities by:
 - Describing the appropriateness of selection of patients for treatment with vernakalant IV, monitoring of patients during and after vernakalant IV administration, and use of anti-arrhythmics before and after vernakalant IV, as consistent with the label and risk minimisation activities (health provider educational card).
 - Monitoring for the occurrence and incidence SAEs and HOIs to review with the EU Regulatory Agency with respect to risk minimisation activities.

2.2 Secondary Objectives

The secondary objectives of the study are to:

1. Summarise the count and rate of all SAEs for HOIs that may not meet the definitions of medically significant HOIs, as well as all other SAEs reported during treatment and during the first 24 hours after the last infusion of vernakalant IV or until discharge/end of medical encounter, whichever occurs earlier.
2. Characterise patients administered vernakalant IV in terms of patient demographics, medical history, and presenting conditions. Specific conditions to be summarised include:

- Heart failure, New York Heart Association (NYHA) functional class
- Prolonged QT, severe bradycardia, sinus node dysfunction, second or third degree heart block, clinically meaningful valvular stenosis, hypertrophic obstructive cardiomyopathy, restrictive cardiomyopathy, constrictive pericarditis
- History of hyperthyroidism
- Severe aortic stenosis, low systolic blood pressure (BP)
- Recent acute coronary syndrome (including myocardial infarction [MI])
- Presence of pacemaker/year of implantation
- Hepatic impairment

3. Document the administration of concomitant treatment modalities to restore or maintain sinus rhythm during the hospitalisation/medical encounter (e.g., oral or IV anti-arrhythmics, electrical cardioversion, ablation, Maze procedure).
4. Describe the rate of successful cardioversion to sinus rhythm for at least one minute within 90 minutes of start of first vernakalant IV administration and time (in hours) from vernakalant infusion until discharge/end of medical encounter.

3 STUDY OUTCOMES AND DEFINITIONS

3.1 Health Outcomes of Interest (HOI)

3.1.1 Significant Hypotension

Significant hypotension is defined as symptomatic hypotension with systolic BP <90 mmHg, requiring treatment with vasopressors.

3.1.2 Significant Ventricular Arrhythmia

Significant ventricular arrhythmia is defined as

- Sustained ventricular tachycardia (VT) with a ventricular heart rate > 120 beats per minute with duration > 30 seconds or VT that required intervention with either electrical shock or anti-arrhythmic drugs, or
- Torsade de Pointes with a duration of >10 seconds, or
- Ventricular fibrillation of any duration.

3.1.3 Significant Atrial Flutter

Significant atrial flutter is defined as atrial flutter with 1:1 atrioventricular conduction of >10 seconds duration and a ventricular rate of >200 beats per minute (bpm).

3.1.4 Significant Bradycardia

Significant bradycardia is defined as bradycardia requiring electrical pacing (temporary or permanent) or any other SAEs involving bradycardia.

It is anticipated that rates of HOIs may be somewhat higher in this real-world study setting compared to rates observed in the vernakalant clinical trial program due to the selective patient entry criteria of these randomized clinical trials. Likewise, comparisons to the published literature are not planned and would prove difficult due to differences in case definitions for each specific HOI and variability of reported follow-up periods from administration of a given study drug or intervention to time of the event. However, the frequency of HOIs will be carefully monitored by the Sponsor, the Contract Research Organisation (CRO), and the independent Safety Review Committee (SRC) throughout the duration of the study.

3.2 Safety Outcomes

3.2.1 Adverse Events (AEs)

AE is defined as any untoward medical occurrence in a patient administered a pharmaceutical product at any dose that does not necessarily have a causal relationship with vernakalant IV treatment. An AE can therefore be any unfavourable and unintended sign (including an abnormal laboratory finding, for example), symptom, or disease temporally associated with the use of the medicinal product, whether or not considered related to the pharmaceutical product. This definition includes intercurrent illnesses or injuries and exacerbation of pre-existing conditions.

If the onset of an event occurred before the patient entered the study (e.g., any pre-planned hospitalisation or non-emergency routine visits for a pre-existing condition), the condition or pre-existing condition would not be considered an AE unless it worsened following medicinal product use or hospitalisation was prolonged due to a worsening of the pre-existing condition.

A pre-existing condition is a clinical condition (including a condition being treated) which is diagnosed prior to use of a Cardiome product or protocol-specified intervention, and which is documented as part of the patient's medical history (e.g., pre-planned hospitalisation or a routine visit for the pre-existing condition). Any worsening of a pre-existing condition temporally associated with the use of a Cardiome product is by definition an adverse event.

3.2.2 Serious Adverse Events (SAE)

An SAE is defined as an AE which is fatal or life threatening, results in persistent or significant disability, requires inpatient hospitalisation, prolongation of existing inpatient hospitalisation, or is a congenital anomaly, cancer, the result of an overdose or is another important medical event. Other important medical events that may not result in death, may not be life-threatening, or may not require hospitalisation may be considered a SAE when based upon appropriate medical judgment, they may jeopardise the patient or subject and may require medical or surgical interventions to prevent one of the other outcomes listed previously.

Specifically, the SRC is responsible for (1) review of individual patient listings of SAE reports and aggregated data in data tables and study result reports; (2) periodic assessment of subject accrual rate and study status; (3) evaluation on an ad hoc basis of any urgent safety issue identified by the Sponsor, CRO or the SRC, and (4) documentation and communication in writing of all SRC activities to Sponsor. Source documentation routinely collected for the study

which may include ECG tracings corresponding to arrhythmic events if performed as part of standard of care is also provided to the SRC for review of individual HOIs and SAEs.

3.2.3 Non-Serious Adverse Events

AEs which do not meet the above criteria are defined as **non-serious adverse experiences (NSAE)**. For regulatory reporting requirements in the European Union, SAEs and NSAEs that are at least possibly drug related are defined as serious adverse reactions (SADR) and non-serious adverse reactions, respectively.

3.3 Effectiveness Outcome: Conversion to Sinus Rhythm

Effectiveness of vernakalant IV will be assessed as a secondary endpoint, defined as the proportion of patients who are converted to sinus rhythm for at least one minute within 90 minutes of start of first vernakalant IV administration. Additionally, the proportion who are converted to sinus rhythm regardless of timing will be reported. (Refer to Section 4.3 for description of further effectiveness subgroup analyses per Summary of Product Characteristics (SmPC)).

3.4 Derived Variable Definitions

The following derived/calculated values will be used:

- Age at enrolment = [(date of informed consent – date of birth) + 1]/365.25, or self-reported age if date of birth is not available.
- BMI = Weight (Kg)/Height (m)². English standard units should be converted to international or metric units.
- (S)AE or HOI onset in days and time (in hours or minutes) following vernakalant IV infusion = date/time of onset or (S)AE-date – date/time of start of first infusion.
- Duration or period = (stop time – start time). Note there are key durations that include, but are not limited to, duration of vernakalant IV infusions and duration of HOI and SAE.
- Vernakalant IV dose per body weight = vernakalant IV dose (mg) / body weight (kg).
- Duration of time to conversion to sinus rhythm = (date/time of conversion to sinus rhythm – date/time of start of first infusion).
- Percentage of weight-based dosing recommendation per label (%) = (Vernakalant IV dose [mg/kg] / Recommended vernakalant IV dose [mg/kg]) * 100. Range from 0% to above 100%, with 100% indicating that dose is equal to recommended dose, calculated per first or second infusion. Patients with cumulative doses greater than the maximum recommended dose will be noted (overall and for first and second infusion, separately).
- Duration of current AF in hours = (Vernakalant administration date/time - AF onset date/time).

- Time since first AF diagnosis = (Start date of Vernakalant IV administration - Date of first AF diagnosis).
- Rate of conversion to sinus rhythm for at least one minute within 90 minutes of start of first vernakalant IV administration = (Number of relevant patients converted to sinus rhythm for at least one minute within 90 minutes of start of first vernakalant IV administration) / (Total number of relevant patients administered vernakalant IV). Rate of conversion can be evaluated based on different types of patients, e.g. all patients receiving vernakalant IV or all such patients with other restrictions.
- Elevated liver enzymes (inclusive of possible abnormal liver function or liver injury) = an increase above upper limit of normal (ULN) for alanine aminotransferase (ALT), aspartate aminotransferase (AST), or total bilirubin (TB) or conjugated bilirubin. [1,2]
- Total hospital length of stay (hours) = (Date/time of discharge or release of facility – Date/time of hospital admission).
- Modification of Diet and Renal Disease (MDRD) estimated Glomerular Filtration Rate (GFR) (mL/min per 1.73 m²) = $186 \times (\text{Serum creatinine } [\text{Scr}])^{-1.154} \times (\text{Age})^{-0.203} \times (0.742 \text{ if female}) \times (1.210 \text{ if Black})$. [2]
- Time between Current and Previous Study Enrolment = (Informed consent date of current enrolment – Informed consent date of previous study enrolment).

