5 STATISTICAL ANALYSIS

Categorical variables (e.g., gender) will be summarised by the number and percentage (%) of patients. For the pre-specified HOIs, both stratified (based on enrolment method, i.e. prospective or retrospective) and unstratified (i.e. overall) cumulative incidences will be reported, and corresponding 95% confidence intervals will be displayed for each such specific HOI. Unless otherwise specified, the 95% confidence intervals around the proportions will be calculated using exact methods described by Clopper and Pearson [3].

Continuous variables (e.g., age) will be summarised using descriptive statistics (number of non-missing values, mean, standard deviation, median, Q1 and Q3, minimum and maximum values).

Some continuous variables will be described using categorizations to provide additional detailed information regarding vernakalant IV administration. For instance, percentage of weight-based dosing recommendation may be described using the following categories: < 70%, 70% to < 85%,

85% to < 95%, 95% to 105%, > 105% to 110%, > 110% and the duration of infusion will be reported in categories such as: < 7 minutes, 7 minutes to < 9 minutes, 9 minutes to 11 minutes, >11 minutes to 13 minutes, > 13 minutes. The categorizations will be based on the empirical data and may be adjusted.

Key results will be presented overall and by patient enrolment method (i.e. prospective or retrospective). Any changes to the analysis over the course of the study will be described in Statistical Analysis Plan (SAP) addendums or amendments. Ad hoc analyses (by country, site, or other) will be performed as requested by the sponsor.

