5.1.3 Patient Demographics

The following demographics characteristics will be summarised for enrolled patients in the analysis set (**Table 4.1**):

- Gender (male, female)
- Age (years) at Informed Consent date
- Race or ethnicity as recorded in the medical record, if available (White, Black, Hispanic, Asian, other). Note: Patients may have more than one race recorded.
- Body weight (Note: Patient weights were either obtained from medical record or were prospectively collected after administration of vernakalant IV in a supplemental data collection tool for prospectively enrolled patients.)
- Method of measurement for weights (direct measurement, patient-reported, estimated from health professional, unknown, recorded after vernakalant IV administration)
- Reason patient weight not measured prior to vernakalant IV administration (patient bed-bound, weighing equipment unavailable or broken, unknown, other)
- Body mass index (BMI)

Gender and age will also be summarised for screened patients and for screened but not enrolled patients (**Table 4.2**):

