For the 2-<4 hour time interval, the number of patients with at least HOI with an onset date and time in the 2-<4 hour interval (interval is from 2:00:00 following start date and time of vernakalant administration to 3:59:59 following start date and time of vernakalant administration) divided by the number of patients enrolled and treated with vernakalant.

For 4-24 hour time interval, the number of patients with at least one HOI with an onset date and time in the 4-24 hour interval (interval is from 4:00:00 following start date and time of vernakalant administration to 24:00:00 following start date and time of vernakalant administration) divided by the number of patients enrolled and treated with vernakalant

Characteristics of patients with HOIs, which may include prior medical history, presenting conditions, medication use, dosing/administration of vernakalant IV, concomitant therapies, and assessment of relatedness as provided by the investigator will be summarised as a narrative in the listing of individual HOI events in study reports. Case narratives will be provided in **Listing 1b** and **Listing 2b** for each HOI and SAE regardless of the relationship to vernakalant and will describe patients with more than one HOI event reported. Listings will be by-event (i.e., patient with multiple events will be repeated for each event type) and will contain the patient's case narrative for each event type.

5.5 Primary Objective #2: Administration of Vernakalant Consistent with Weight-Based Dosing and Patient Monitoring

Based on Primary Objective #2, distributions of patient body weight, number of infusions, total dose administered with each IV infusion and administration duration stratified by body weight (<113 kg and \geq 113 kg) will be summarised (**Table 9**). Body weight and details of dosing and administration (indication, number of infusions, dose in mg and mg/kg, percentage of weight-based dosing recommendations, duration, whether stopped prematurely, and the reasons for stopping) will be presented separately for each body weight group.

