| Black | xx (xx.x%) | xx (xx.x%) | xx (xx.x%) |
| Hispanic | xx (xx.x%) | xx (xx.x%) | xx (xx.x%) |
| Asian | xx (xx.x%) | xx (xx.x%) | xx (xx.x%) |
| Other | xx (xx.x%) | xx (xx.x%) | xx (xx.x%) |
| Missing | xx | xx | xx |
| Body weight (kg)² | | | |
| n | XXX | XXX | XXX |
| Mean (SD) | xx.x (xx.xx) | xx.x (xx.xx) | xx.x (xx.xx) |
| Median | xx.x | xx.x | xx.x |
| Q1, Q3 | xx.x, xx.x | xx.x, xx.x | xx.x, xx.x |
| Min, Max | xx.x, xx.x | xx.x, xx.x | xx.x, xx.x |
| Missing | xx | xx | xx |
| Source of weight measurement as recorded in medical record | | | |
| n | xx | xx | xx |
| Direct measurement | xx (xx.x%) | xx (xx.x%) | xx (xx.x%) |
| Patient-reported | xx (xx.x%) | xx (xx.x%) | xx (xx.x%) |
| Estimated by Health Professional | xx (xx.x%) | xx (xx.x%) | xx (xx.x%) |
| Unknown method of ascertainment | xx (xx.x%) | xx (xx.x%) | xx (xx.x%) |
| Other | xx (xx.x%) | xx (xx.x%) | xx (xx.x%) |
| Missing | xx | xx | xx |
| Body weight collected after vernakalant administration (kg)² | | | |
| n | XXX | XXX | XXX |
| Mean (SD) | xx.x (xx.xx) | xx.x (xx.xx) | xx.x (xx.xx) |
| Median | xx.x | xx.x | xx.x |
| Q1, Q3 | xx.x, xx.x | xx.x, xx.x | xx.x, xx.x |
| Min, Max | xx.x, xx.x | xx.x, xx.x | xx.x, xx.x |
| Missing | xx | xx | xx |
| Reason patient's weight not collected prior to vernakalant IV administration³ | | | |

| Characteristic | Analysis Set (N = xxx) | Prospective Patients (N = xxx) | Retrospective Patients (N = xxx) |
|--|---------------------------|-----------------------------------|-------------------------------------|
| n | xx | xx | xx |
| Patient bed-bound | xx (xx.x%) | xx (xx.x%) | xx (xx.x%) |
| Weighing equipment unavailable or broken | xx (xx.x%) | xx (xx.x%) | xx (xx.x%) |
| Unknown | xx (xx.x%) | xx (xx.x%) | xx (xx.x%) |
| Other | xx (xx.x%) | xx (xx.x%) | xx (xx.x%) |
| Missing | xx | xx | xx |
| BMI | | | |
| n | xxx | xxx | xxx |
| Mean (SD) | xx.x (xx.x) | xx.x (xx.x) | xx.x (xx.x) |
| Median | xx.x | xx.x | xx.x |
| Q1, Q3 | xx.x, xx.x | xx.x, xx.x | xx.x, xx.x |
| Min, Max | xx.x, xx.x | xx.x, xx.x | xx.x, xx.x |
| Missing | xx | xx | xx |

Note: Total n for each variable includes non-missing observations. Percentages, where applicable, are calculated with non-missing observations in denominator unless otherwise noted.

¹Patients may select more than one race category.

²Patient weights were either obtained from medical record or were prospectively collected after administration of vernakalant.

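### Table 9 gives percentage of recommended dose pooled over measured and unmeasured body weights, although weight source is collected: a cheap improvement would show the directly measured weights separately

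*SAP*

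**What the plan says.** SAP 3.4 defines "Vernakalant IV dose per body weight = vernakalant IV dose (mg) / body weight (kg" and derives from it the percentage of the label dose, without saying which weight is meant.

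SAP 5.1.3 records several kinds of weight: "Method of measurement for weights (direct measurement, patient-reported, estimated from health professional, unknown, recorded after vernakalant IV administration". It adds that "Patient weights were either obtained from medical record or were prospectively collected after administration of vernakalant", the latter for prospectively enrolled patients. Table 4.1 has a row headed "Source of weight measurement as recorded in medical record" and a separate block headed "Body weight collected after vernakalant administration (kg". The second block has no row for method of measurement.

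For Primary Objective 2, SAP 5.5 summarises "total dose administered with each IV infusion and administration duration stratified by body weight", split at 113 kg. Tables 9.1, 9.2 and 9.3 repeat this for all, prospective and retrospective patients. The percentage bands in SAP 5 include "85% to < 95%, 95% to 105%, > 105% to 110%, > 110" per cent. Listing 5d covers infusions above 105% and prints mg and mg/kg. Listing 1a flags doses above 110% in patients with an HOI and prints mg/kg only. Neither listing shows weight source.

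**The concern.** Primary Objective 2 describes dosing in order to look for overdose and medication error, and a wrong weight is one route to both. The percentage of recommended dose compares the dose with a recorded weight. With a directly measured weight, that is a reasonable check on whether the dose suited the patient. With a reported or estimated weight that was also used to work out the dose, the two sides of the ratio share the same error, and the result is close to 100% whatever the patient really weighed.

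Table 9 adds these two kinds of result together. Table 4.1 gives the share of each source, but the shares alone do not let a reader separate the dose results. A reassuring pooled table could rest partly on agreement that arises by construction. Primary Objective 3 draws on the same dosing results (SAP 5.6).

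**Working it through.** **Inputs.** Recommended dose (SAP 5.5): 3 mg/kg then 2 mg/kg below 113 kg; 339 mg then 226 mg at 113 kg or more. Percentage definition: SAP 3.4. Target of 2,000: SAP 4.1. The documents do not give the share of weights that were measured, the size of weight errors, or which weight set the dose.

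**1. The SAP's own examples.** 2.5 / 3 = 83.3% and 350 / 339 = 103.2%. Both reproduce. The caps agree with the 113 kg limit: 3 x 113 = 339 and 2 x 113 = 226.

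**2. Why a shared weight error cancels.** Let r be the recorded and t the true weight, both below 113 kg. Assume the dose was set from r, so dose = 3r.
- Percentage in Table 9: 3r / 3r = 100%.
- Percentage against true weight: 3r / 3t = r / t.
- Example: a 70 kg patient recorded and dosed as 80 kg receives 240 mg. Table 9 shows 100%; the true figure is 240 / 210 = 114.3%.
- In the other direction, 70 kg recorded as 60 kg gives 180 / 210 = 85.7%, again shown as 100%.

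Splitting by source does not recover this error. It only shows where the error could lie.

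**3. What stays visible with any source.**
- Arithmetic slip: recorded weight 70 kg, 240 mg given. 240 / 210 = 114.3%, reported as such.
- Regimen slip: a second infusion given at 3 mg/kg. 3 / 2 = 150%.
- Cap: at 113 kg or more the recommended dose is fixed, so 350 mg gives 103.2% whatever the exact weight.

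**4. What pooling hides.** Let f be the share with a measured weight, a the rate above 110% among them, b the rate among the rest, and x the pooled rate. Then x = f a + (1 - f) b. With b unknown and x small, a can lie anywhere from 0 to x / f. For an assumed x = 2%:

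| f (assumed) | Range for a |
|---|---|
| 25% | 0 to 8.0% |
| 50% | 0 to 4.0% |
| 75% | 0 to 2.7% |

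**5. Precision of a measured-only summary.** Clopper-Pearson 95% limits at an observed 1.0%:
- 5 / 500: 0.33% to 2.32%
- 20 / 2,000: 0.61% to 1.54%

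These agree with SAP Table A, row 0.010 (0.003, 0.023 and 0.006, 0.015). The 500 is an assumed share of 25%.

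**6. Listings.** A dose flagged above 110% in Listing 1a is also above 105%, so the patient appears in Listing 5d. There the weight follows as mg divided by mg/kg. The source does not follow from either listing.

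**The case against.** The plan delivers what was promised. Primary Objective 2 is descriptive, Protocol 10.2 asks for dose by body weight and by enrolment method, and Tables 9.1-9.3 provide both. The study mandates no procedures, so unmeasured weights are a disclosed limit of the data. Source is shown in Table 4.1, overall, by enrolment method and by country, and SAP 5 allows ad hoc breakdowns on request. All of this stands. It makes the point an added tabulation, not a departure from the protocol. It does not supply the cross-tabulation, and none by weight source is pre-specified.

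Four stronger readings are tempting, and the documents do not support them.
- *That Table 9 conceals a material number of overdoses.* Neither the frequency of unmeasured weights nor the size of their errors is given, and neither document states that the recorded weight set the dose.
- *That the SAP's reasons for a missing pre-dose weight show how often doses rested on reported or estimated weights.* The item reads "Reason patient weight not measured prior to vernakalant IV administration (patient bed-bound, weighing equipment unavailable or broken, unknown, other", but Table 4.1 footnote 3 limits it to patients with no weight in the medical record. It says nothing about the frequency of reported or estimated weights.
- *That splitting would reveal the hidden errors.* It would not, as step 2 shows.
- *That overdose flags in HOI patients cannot be traced.* They can, through Listing 5d; only the source label is missing.

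The contrast between sources is also not clean. Table 4.1 shows no date for a directly measured record weight, and an unknown method may include measured weights.

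**Conclusion.** The point holds as a cheap improvement. The dose percentages are pooled over weight sources that support different conclusions, and a field that separates them is already collected. For reported or estimated weights, a value near 100% may mean only that dose and record agree. This rests on the inference that the recorded weight set the dose, which is natural for weight-based dosing but not stated.

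The size cannot be determined from the documents. The ranges in step 4 are bounds under assumed shares and an assumed pooled rate, not estimates. No HOI incidence and no test depends on this, and the pooled bands still pick up errors of arithmetic, regimen and cap.

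**What to change.** Keep Tables 9.1-9.3 as they are. In the overall tables only, not in the country repeats, add the percentage-of-recommendation bands for three groups:
1. directly measured medical-record weight;
2. post-administration weight;
3. all other sources (patient-reported, estimated, unknown, other).

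Use group 1 as the sensitivity summary for overdose. Do not add group 2 to it, because Table 4.1 has no method row for those weights. State beside group 3 that weight error there cannot be detected. Add a weight-source column to Listings 5d and 1a. To make the groups unambiguous, add a sentence to SAP 3.4 saying when the post-administration weight is the denominator.

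The cost is extra rows and two listing columns from data already collected, with smaller cells and the wider interval in step 5. The measured patients may also be a selected group, for example with fewer bed-bound patients, which is why the pooled tables should stay.
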